## 6.0 TREATMENT AND EVALUATION OF ENDPOINTS

For this Registry, the following definitions apply:

- **Index procedure:** the entire intervention to treat the subject's peripheral vascular thrombosis. A subject's procedure may include more than one session if the subject is removed from the interventional suite and placed in a holding area with the intention of returning to the suite for additional treatments either the same day or following day (e.g., catheter placement or removal for CDT). An index procedure can start with JETi or any other treatment first.
- **Treatment:** the individual techniques performed during a procedure to address the subject's peripheral vascular thrombosis (e.g., JETi thrombectomy, balloon angioplasty, stent placement, or catheter-directed thrombolysis (CDT)). Note that "JETi treatment" will refer to treatment during which the JETi Thrombectomy device is used.

NOTE: A subject's treatment is determined by the treating physician based on the clinical situation and institutional practices.

- **Session:** a session is the in and out period within an interventional suite that a subject is receiving treatment. A subject's procedure may include more than one session if the subject is removed from the interventional suite and placed in a holding area with the intention of returning to the suite for additional treatments either the same day or following day (e.g., catheter placement or removal for CDT).

---

 Specifically Lower Extremity DVT subjects as defined in Appendix II

NOTE: Treatment for unexpected re-thrombosis is an adverse event and should not be considered as an additional session of the initial procedure.

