#### **2.2.2 Indication for Use**

##### **JETi Hydrodynamic Thrombectomy System (JETi HTS) – US**

The JETi Hydrodynamic Thrombectomy System is intended to remove/aspirate fluid and break-up soft emboli and thrombus from the peripheral vasculature and to subselectively infuse/deliver diagnostics or therapeutics with or without vessel occlusion.

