## 4.0 ENDPOINTS

### 4.1 Primary Endpoints

#### 4.1.1 Arterial Subjects

For subjects treated for arterial thrombosis (may include diagnoses such as acute limb ischemia, chronic limb ischemia/chronic limb threatening ischemia, peripheral artery disease, etc.) or arteriovenous (AV graft, AV fistula) thrombosis, all endpoints are descriptive.

There will be no hypothesis testing, and there are no statistical power considerations. For subjects treated for arterial or arteriovenous thrombosis, the primary endpoints are:

- **Clot removal grade** for each JETi-treated target vessel(s) from pre-JETi angiogram to post-JETi angiogram (post-JETi thrombectomy and prior to any adjunctive therapies to treat underlying culprit lesions) per the grades in **Table 1** (vessel basis). The independent imaging core laboratory will be responsible for assessing this endpoint.
- **Composite of JETi-related major adverse events (MAEs)**, defined as the following JETi-related events: device-related death, major amputation of the treated limb (arterial subjects only),

or major bleeding up to 30 days post-JETi procedure and as adjudicated by a clinical events committee (CEC) (subject basis). Refer to **Appendix II** for definitions of major adverse events.

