#### 4.2.3 Venous Subjects

- Percent of treated vessels with ≥75% clot reduction from pre-JETi venogram to post-JETi venogram (post-JETi thrombectomy and before any adjunctive therapies to treat underlying culprit lesions) via modified Marder score. The independent imaging core laboratory will be responsible for assessing this endpoint.
- For subjects not treated for lower extremity DVT as defined in Appendix II (i.e., upper extremity DVT (UE DVT)), Clot removal grade for each JETi-treated target vessel from pre-JETi venogram to final venogram (post-JETi thrombectomy and after any/all adjunctive therapies and prior to removal of the vascular sheath) per the grades in Table 1.

 de Donato G, Pasqui E, Sponza M, et al. Safety and Efficacy of Vacuum Assisted Thrombo-Aspiration in Patients with Acute Lower Limb Ischaemia: The INDIAN Trial. *Eur J Vasc Endovasc Surg.* 2021;61(5):820-828. doi:10.1016/j.ejvs.2021.01.004

- Components of the JETi-related MAE up to 30 days post-JETi adjudicated by a CEC including death, symptomatic pulmonary embolism (PE), major bleeding, and re-thrombosis of JETi treated vessel(s).
  - Re-thrombosis of the JETi-treated vessel(s) at 30-day, and 12-month follow up, as assessed by investigator/physician reported, and as adjudicated by CEC.
  - The Villalta Post Thrombotic Syndrome (PTS) severity scale at baseline, 30-day, and 12-month follow-up. Note that this assessment will apply only to subjects with lower extremity DVT.
    - Edema component score from the Villalta Post Thrombotic Syndrome (PTS) severity scale at baseline, 30-day, and 12-month follow-up
  - A 7-point Likert Scale for leg pain at baseline, discharge, 30-day, and 12-month follow-up.
  - Venous patency and compressibility as determined by duplex ultrasound at baseline 30-day, and 12-month follow-up.
  - Acute success, [REDACTED] assessed by core laboratory:
    - Device success: post-JETi thrombus removal grade II-III [REDACTED]
    - Technical success: Final thrombus removal grade II-III, [REDACTED] where final [REDACTED] evaluation occurs after JETi system and any other adjunctive device or procedures.
    - Procedural success: Technical success with no JETi-related MAEs within 5 days of registration or by discharge, whichever occurs first.
- If no adjunctive therapies or devices are used after JETi, post-JETi [REDACTED] score is also final [REDACTED] score.
- [REDACTED]

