### 6.1.2 Index Procedure

The thrombectomy procedure with the JETi System should be conducted in accordance with standard of care practice and approved labelling. All consented subjects that have a successful or attempted (with at least the JETi Catheter being introduced into the intended vasculature) procedure with the JETi System will be considered registered subjects and will be entered into the study.

The following procedural data will be collected:

- Procedure information (including, but not limited to): Start and end dates/times, amount of contrast used during the entire procedure, total fluoroscopy time, access sites, obstruction location, and the number of sessions within the procedure (If multiple sessions were needed, the location of the subject in between the sessions is requested), procedure outcome.
- Treatment information (including, but not limited to): The treatments performed during the index procedure will be captured in the order of performance with specific details for each treatment. The treatment options will include the following:
  - JETi mechanical thrombectomy (MT) only
  - JETi in combination with one or more of the following treatments [REDACTED]

- Imaging Assessments
  - Pre-JETi arteriogram: The pre-JETi arteriogram will be used to assess the initial degree of clot burden after catheter insertion into the vascular system and prior to JETi thrombectomy.
  - Post-JETi arteriogram: The post-JETi thrombectomy arteriogram will be used to assess the degree of clot removal after JETi thrombectomy and prior to any adjunctive therapies used to treat underlying culprit lesions.
  - Final arteriogram: The final angiogram will be completed to assess the degree of clot removal after JETi thrombectomy and any/all adjunctive therapies and prior to removal of the vascular sheath.

All treated vessels will be assessed using the provided grades in **Table 1**, per core lab assessment.

All treated arterial vessels will be assessed using the provided TIPI grades in Table 3, per core lab assessment.

- Acute success, as per TIPI score (**Table 3**), per core lab assessment:
  - Device success: Near complete or complete recanalization of occluded vessel, defined as post-JETi TIPI 2-3.
  - Technical success: Near complete or complete recanalization of occluded vessel, defined as final TIPI 2-3, where final TIPI evaluation occurs after JETi system and any other adjunctive device or procedures.

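### Arterial device success counts flow that an earlier treatment had already restored, and loose image timing can also let another therapy's effect into the clot removal grade and the venous post-JETi endpoint

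*Protocol*

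**What the plan says.** **Order of treatment.** Protocol section 6.0 says "An index procedure can start with JETi or any other treatment first". The treatments it lists include balloon angioplasty, stenting and catheter-directed thrombolysis (CDT) as well as JETi, and a procedure may run over several sessions into the next day.

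**Pre-JETi image.** Under Protocol 6.1.2 it serves to "assess the initial degree of clot burden after catheter insertion into the vascular system and prior to JETi thrombectomy". Section 6.2.2 has the equivalent for venograms.

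**Post-JETi image.** For the arterial primary endpoint (Protocol 4.1.1, SAP 1.4.1.1) it is "post-JETi thrombectomy and prior to any adjunctive therapies to treat underlying culprit lesions". For the venous post-JETi endpoint (Protocol 4.2.3, SAP 1.4.2.3) it is "post-JETi thrombectomy and before any adjunctive therapies to treat underlying culprit lesions".

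**Arterial device success.** Protocol 4.2.2 and SAP 1.4.2.2 define it as a post-JETi TIPI score of 2 or 3. TIPI is scheduled at two time points, post-JETi and final. By Table 3, a score of 2 needs only partial recanalization with some distal flow.

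**Data and analysis.** Protocol 6.1.2 provides that "The treatments performed during the index procedure will be captured in the order of performance", 6.2.2 says the same for venous subjects, and thrombolytics given during the procedure are recorded. SAP 2.3.1.1 summarizes the arterial grade as the number and percentage of treated vessels. The visible text does not relate treatment order to any outcome.

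**The concern.** The plan deliberately separates what JETi achieves from what the whole procedure achieves: post-JETi against final image, and device against technical success. That separation works only if no other clot-removing therapy can act inside the post-JETi measurement.

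There are two ways in. Device success is a level and not a change, so an earlier treatment feeds straight into it wherever the baseline image is taken. The clot removal grade and the venous reduction are changes, so they depend on which runs are chosen as the pair, and the wording leaves that choice open at both ends. Two sites with the same treatment sequence could submit different image pairs. A reader would then credit JETi with clot that lysis or another device removed. Section 15.1 of the protocol raises the possibility of thrombus removal without thrombolytic drugs, and a mixed figure cannot inform that.

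**Working it through.** There is no planned figure to reproduce. The arterial endpoints carry no hypothesis test or power statement, and the derivation of the sample of about 280 is redacted. The check is one of wording, followed by illustrative arithmetic.

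**1. Which images qualify?**
- Sequence CDT, then JETi. A run before CDT and a run just before JETi are both taken before JETi, and both can fit the pre-JETi description. The word initial leans towards the first. The text does not choose.
- Sequence JETi, CDT, JETi, stent. The run before the stent follows JETi and precedes culprit-lesion therapy. Read literally it is post-JETi, although CDT lies inside the interval.
- Lytic infused through the device. The US indication (Protocol 2.2.2) includes use to "subselectively infuse/deliver diagnostics or therapeutics with or without vessel occlusion", and section 6.0 treats any treatment in which the device is used as JETi treatment. Lysis given this way is not separated out.

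**2. Clot removal grade.** Let an earlier treatment remove fraction a of the clot and JETi remove fraction b of the remainder (both assumed). With the baseline after the earlier treatment the reduction is b. With the baseline before it the reduction is 1 − (1 − a)(1 − b). Grades follow Table 1.

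| a | b | Baseline after | Baseline before |
|---|---|---|---|
| 0.4 | 0.4 | 40%, Grade I | 1 − 0.6 × 0.6 = 64%, Grade II |
| 0.6 | 0.9 | 90%, Grade II | 1 − 0.4 × 0.1 = 96%, Grade III |
| 0.6 | 0 | 0%, Grade I | 1 − 0.4 × 1 = 60%, Grade II |
| 0.2 | 0.7 | 70%, Grade II | 1 − 0.8 × 0.3 = 76%, Grade II |

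The choice of run can move a vessel by a grade, but need not.

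**3. Arterial device success.** Let p be success with JETi alone, s the share of vessels with another clot treatment before the post-JETi image, and r the share of JETi failures which that treatment rescues. If s is unrelated to whether JETi would have failed, observed success is p + s·r·(1 − p), and the overstatement is s·r·(1 − p). All three are assumptions. The values 0.76 and 0.85 echo success rates cited in Protocol 1.0 (JETi alone in a venous series; all interventions using JETi in an arterial review) and are only plausible settings.

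| p | s = 0.10, r = 0.5 to 1 | s = 0.50, r = 0.5 to 1 |
|---|---|---|
| 0.50 | 2.5 to 5.0 points | 12.5 to 25.0 points |
| 0.76 | 1.2 to 2.4 points | 6.0 to 12.0 points |
| 0.85 | 0.8 to 1.5 points | 3.8 to 7.5 points |

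Lowest: 0.10 × 0.5 × 0.15 = 0.0075. Highest: 0.50 × 1 × 0.50 = 0.25.

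**4. What tighter image timing would do.** With the baseline just before JETi and the post-JETi run before any other therapy, the grade reflects b alone (40%, Grade I, in the first row), apart from lytic given during JETi. For device success, timing removes the effect of later therapy only. An earlier treatment still counts, because TIPI 2 or 3 is an absolute level. That part needs a split by treatment order.

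**The case against.** The strongest reply is that the wording is loose but the intent is clear. Protocol 4.2.2 says that when no adjunctive therapy or device follows JETi, the post-JETi TIPI score also serves as the final one, and technical success is read after any other adjunctive device or procedure. That sets post-JETi before every adjunct, with no culprit-lesion limit. Section 4.1.2 attaches the same culprit-lesion phrase to the final venogram, where it can hardly be meant to exempt lysis. The catheter in the pre-JETi description could also be the JETi catheter, which would place the baseline after any earlier treatment. Core laboratory guidelines, supplied separately, may settle the timing. All this stands as evidence of intent. It is a reason to put the rule into the definitions, not evidence that the definitions already contain it.

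For device success, the definition speaks of an occluded vessel, which might imply occlusion before JETi. But a vessel occluded on arrival, opened by lysis and then treated with JETi still satisfies the score.

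Three stronger readings are tempting and not supported:
- That prior lysis necessarily counts in the arterial primary endpoint. The grade is a pre-to-post change, so prior lysis enters only if the baseline run was taken before it.
- That no analysis isolates JETi. Protocol 8.5 refers subgroups to the SAP, whose visible numbering runs from 2.3.2 to 2.6 and then to 2.9. The treatment lists and parts of venous device success are redacted.
- That 24% measures the problem. In Protocol 1.0 that is CDT given after JETi in an 18-patient venous series, and says nothing about earlier or interposed lysis in arteries.

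**Conclusion.** The point holds for arterial device success as written: an earlier treatment that restores flow is counted as JETi success, whichever run is the baseline. For the arterial clot removal grade and the venous post-JETi endpoint, the visible rules permit another therapy's effect to be included but do not require it.

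The size is unknown. The 0.8 to 25 points for device success rest entirely on assumed values of p, s and r, and on the other treatment being given independently of whether JETi would fail. If it goes mainly to failing vessels, the overstatement for a given s would be larger. The affected endpoints are descriptive, so the consequence is misattribution. Nothing here bears on type I error, on power or on a success decision. The venous primary endpoint is read on the final venogram after all adjuncts by design and is not meant to isolate JETi. It is outside this point.

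**What to change.** These are changes to measurement and analysis only, in Protocol 4.1.1, 4.2.2, 4.2.3, 6.1.2 and 6.2.2 and in the SAP, with the core laboratory guidelines aligned.

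1. Define pre-JETi as the last available run before the first JETi activation.
2. Define post-JETi as the run after JETi and before any other adjunctive therapy or device, whether directed at thrombus or at a culprit lesion.
3. State how mixed sequences are scored. For JETi, other therapy, JETi, one option is to use the run after the last JETi pass and flag the vessel as combined; scoring before the other therapy would discard the second pass. Flag lytic infused through the JETi System as combined too.
4. From the treatment order and thrombolytic data already collected, report the arterial clot removal grade, arterial device success and the venous post-JETi endpoint separately for vessels with and without another thrombus-directed treatment before the post-JETi image, unless a redacted SAP section already does so.

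For subjects already treated, the split in item 4 is enough. While editing, reconcile Protocol 6.1, which places the arterial pre-JETi catheter in the venous system, with 6.1.2.

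The cost is some wording and one table split, with no new data. The JETi-only stratum will be smaller, and its figure may be slightly less favourable.

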Anticoagulants, and antiplatelet medications will be collected for this Registry at Baseline, Index Procedure, Discharge, and all follow-up timepoints. Thrombolytics used during the procedure will be collected. At Baseline, the medications taken within the 30 days prior to the admission and those medications that the patient was taking upon admission will be documented.

AEs experienced by the patient during the study will be reported, please refer to AE reporting section 7.3.1 for additional details of event reporting.

The schedule of events for arterial subjects is located in **Section 6.1.6**

Data collection at each timepoint is discussed in the sections below.

### 6.1.1 Baseline

Subject preparation will occur in accordance with standard hospital policy for the care of interventional endovascular procedures. Note that no data will be recorded until consent is obtained. The following data will be collected:

- Enrollment
- Demographics – including date of birth (US subjects only)/age, sex, race/ethnicity
- Medical history – subject medical history including general medical history, surgical history, vascular history, renal history, DVT history, and thrombotic condition
- Medications: anticoagulant, antiplatelet, and thrombolytic medications (if applicable) taken within the 30 days prior to admission
- Laboratory assessments (within 14 days prior to the JETi procedure):
  - eGFR
  - Serum Creatinine (SCr)
  - Blood urea nitrogen (BUN)
  - Potassium (K)
  - Hemoglobin (Hgb)
  - Platelets (Plt)
  - International normalized ratio (INR)
  - Prothrombin time (PT)
  - Activated partial thromboplastin time (aPTT)
- Clinical assessment (within 14 days prior to the JETi procedure)– clinical assessment information including height, weight, blood pressure, heart rate, temperature, and respiratory rate
- Physical exam (within 14 days prior to the JETi procedure)
- Quality of life (QOL) questionnaire: SF-12 (not applicable for post-procedure consented subjects)
- ABI \*
- Rutherford category \*

*\* Note: ABI (done within 3 months prior to JETi procedure) and Rutherford assessment (done within 4 days prior to JETi procedure) can be obtained via a non-study physician, including a referring physician; this will not be considered a protocol deviation. In emergent ALI cases, missing ABI at baseline will not be considered a protocol deviation.*

### 6.1.2 Index Procedure

The thrombectomy procedure with the JETi System should be conducted in accordance with standard of care practice and approved labelling. All consented subjects that have a successful or attempted (with at least the JETi Catheter being introduced into the intended vasculature) procedure with the JETi System will be considered registered subjects and will be entered into the study.

The following procedural data will be collected:

- Procedure information (including, but not limited to): Start and end dates/times, amount of contrast used during the entire procedure, total fluoroscopy time, access sites, obstruction location, and the number of sessions within the procedure (If multiple sessions were needed, the location of the subject in between the sessions is requested), procedure outcome.
- Treatment information (including, but not limited to): The treatments performed during the index procedure will be captured in the order of performance with specific details for each treatment. The treatment options will include the following:
  - JETi mechanical thrombectomy (MT) only
  - JETi in combination with one or more of the following treatments [REDACTED]

- Imaging Assessments
  - Pre-JETi arteriogram: The pre-JETi arteriogram will be used to assess the initial degree of clot burden after catheter insertion into the vascular system and prior to JETi thrombectomy.
  - Post-JETi arteriogram: The post-JETi thrombectomy arteriogram will be used to assess the degree of clot removal after JETi thrombectomy and prior to any adjunctive therapies used to treat underlying culprit lesions.
  - Final arteriogram: The final angiogram will be completed to assess the degree of clot removal after JETi thrombectomy and any/all adjunctive therapies and prior to removal of the vascular sheath.

All treated vessels will be assessed using the provided grades in **Table 1**, per core lab assessment.

All treated arterial vessels will be assessed using the provided TIPI grades in Table 3, per core lab assessment.

- Acute success, as per TIPI score (**Table 3**), per core lab assessment:
  - Device success: Near complete or complete recanalization of occluded vessel, defined as post-JETi TIPI 2-3.
  - Technical success: Near complete or complete recanalization of occluded vessel, defined as final TIPI 2-3, where final TIPI evaluation occurs after JETi system and any other adjunctive device or procedures.
  - Procedural success: Technical success with no JETi-related MAEs within 5 days of registration or by discharge, whichever occurs first
- Adverse events

- Medications: Anticoagulant, antiplatelet, and thrombolytic medications administered during the procedure; anticoagulant and antiplatelet treatments within the peri-operative period should follow recommended societal guidelines.

### 6.1.3 Discharge

Discharge is defined as the subject leaving the treating or referral hospital. Discharge will be performed per standard of care. The following data will be collected:

- Adverse events
- Medications: Anticoagulant and antiplatelet medications

### 6.1.4 Follow-up

A window of 10 days to 60 days post JETi procedure is allowed for the 30-day follow-up visit (30 days - 20 days/+30 days), and a window of 5 months to 13 months is allowed for the 12-month (12 months -5 months/+ 1 month) follow-up visit.

- An in-office visit is required for 30-day follow-up visit. If all attempts to have the patient return to the office for an in-office 30-day follow-up visit are unsuccessful, a phone call follow-up will be allowed to collect SF-12 and adverse event data. Protocol deviations will need to be reported for data that could not be collected via phone.
- While an in-person visit is strongly recommended, the follow-up assessments at 12 months may be collected by phone call or virtual visit. Protocol deviations will need to be reported for data that is not collected via phone.

The following data will be collected at the follow-up visit:

- Adverse events
- Medications: Anticoagulant and antiplatelet medications
- ABI\* (30-day visit only)
- Rutherford classification\* (30-day visit only)

\* Note: ABI and Rutherford assessment can be obtained via a non-study physician, including a referring physician; this will not be considered a protocol deviation. ABI and Rutherford are only applicable to lower limb arterial thrombosis.

- QoL questionnaire (SF-12)

